### *Drug Perfusion trajectories*

We will calculate Z scores for remifentanil and norepinephrine rates of perfusion with the mean and standard deviation (SD) of all participants calculated at the same time point - in the following approach:

$$Z_{individual} = \frac{x_{individual} - \mu_{global}}{\sigma_{global}}$$

where  $\chi$  corresponds to the individual rate of perfusion registered,  $\mu$  and  $\sigma$  correspond to the mean and SD of all participants at the same time.

We will use nociception Z scores to define the level of the importance of intraoperative opioid and norepinephrine administration needed to maintain adequate NOL index. Intraoperative administration will be classified as mild or major:

- None : a decrease in Z score < 1 SD,
- Minor: a decrease in Z score  $\geq$  1 SD,
- Major: a decrease in Z score  $\geq$  1.96 SD.

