### **Intraoperative beta-blockers as a opioid-sparing strategy**

The use of esmolol as an adjuvant to general anesthesia has been suggested as an opioid-free potential alternative. Esmolol is an ultra-short acting cardioselective  $\beta_1$ -adrenergic receptor antagonist that plays a crucial role in reducing sympathetic overload induced by numerous perioperative stimuli such as tracheal intubation, intraoperative events, and extubation (Asouhidou and Trikoupi, 2015). Since sympathetic overload generates physiological responses that reflect the patient's pain (Paloheimo et al., 2010), esmolol could serve as a viable alternative to opioids in maintaining hemodynamic stability during general anesthesia (Asouhidou and Trikoupi, 2015). Although esmolol lacks analgesic or anesthetic properties on its own, its combination with propofol or volatile-based anesthesia showed great promise in reducing the intraoperative and postoperative analgesic consumption (Celebi et al., 2014).

Previous studies assessing intraoperative esmolol and its administration based on vital signs have led to inconsistencies and controversies with some studies supporting its use and others disapproving it (Gelineau et al., 2018). However, relying solely on vital signs, such as blood pressure (BP) or heart rate (HR), as a guide for esmolol administration may influence the doses administered as esmolol can lower BP and HR. Thus, this approach might not be ideal as it

could overlook other essential factors and necessitates the adoption of a more comprehensive monitoring system that considers a larger range of parameters.

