## **Hypotheses**

The main hypothesis of this study is to show that patients receiving an intraoperative esmolol infusion during a NOL-guided general anesthesia, will consume a lower amount of intraoperative remifentanyl (mcg.kg-1.h-1) with a reduction of 20 to 30% of intraoperative opioid consumption, without impacting hemodynamic parameters. Upon reproducible nociceptive stimulation such as orotracheal intubation and initial surgical incision, we expect a reduction of the deltaNOL with the administration of esmolol, while still capturing the event on the PMD-200. Finally, once the patient reaches the PACU, we expect a longer time to first opioid, a lower pain score on arrival, a lower opioid consumption, a reduced incidence of PONV, and a shorter PACU stay.

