***Anesthesia maintenance during surgery:***

Nociception management: The remifentanil target controlled infusion will be set at 3 ng.ml prior to the surgical incision, and will be modified according to the NOL index, as described in Figure 1. If the NOL index is > 25 for more than 1 min, we will increase remifentanil TCI by 0.5 ng.ml. This rate will be decreased by steps of 0.25 ng.ml if the NOL index is < 10 for more than 3 min. The minimal remifentanil TCI concentration allowed in the protocol will be 1 ng ml, to ensure a minimal antinociception drug administration in case of inaccuracy of NOL

Index in either group. Furthermore, in the event of a TAM > 120% of its basal level, and despite a NOL Index between 10 and 25, remifentanil will be increased.

Only the **intervention** and **anesthesia maintenance** sections above differ from the usual management of patients under general anesthesia.

In both groups, IV hydromorphone 0.006 mg.kg and ondansetron 4 mg will be administered once pneumoperitoneum is deflated and skin suture is started. Local anesthetic infiltration of the wounds will be performed by the surgical team using a maximum of 30 ml de bupivacaine 0.5%. Remifentanil infusion will be stopped and removed at the start of wound dressing.

Hemodynamic management: Baseline mean arterial blood pressure (MAP) will be defined as the average of three consecutive values taken 1 min apart and determined before the induction of general anesthesia. Intravenous (IV) infusion of norepinephrine will be adjusted to maintain +/- 20% of the baseline values of the pre-anesthesia MAP. Balanced crystalloids will be administered to patients at a rate of 3 ml.kg.h (ABW) throughout the surgery. Intravenous fluid boluses will be administered at the discretion of the anesthesiologist in charge. Perioperative blood management will be done according to guidelines.

Depth of anesthesia management: The maintenance of anesthesia will rely on sevoflurane to reach [0.7–1.2] minimal alveolar concentration (MAC; MAC adjusted to the participant's age) and a BIS index of [40-60]. Sevoflurane will be discontinued when the wound dressing is completed, and participants will be extubated in the operating room and transferred to the post-anesthesia care unit (PACU).

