### **Secondary endpoints**

- The NOL Index variation before and after orotracheal intubation and first surgical incision. NOL index will be evaluated 3 minutes after stimulation to record the maximum value and calculate the area under the curve;
- The mean intraoperative BP and HR;
- The intraoperative doses and time weighted average of norepinephrine (mg); ephedrine (mg), glycopyrrolate (mg) and atropine (mg);
- Total time and time weighted average with NOL value above > 25;
- The total time and time weighted average of hypotension (< 20% of the baseline values of the pre-anesthesia mean arterial pressure (MAP) and/or bradycardia (HR < 60 beats/min, or HR < 50 beats/min for a profound bradycardia)) during surgery;
- The time to first analgesic requirement in PACU;
- The amount of morphine equivalent consumption for postoperative pain relief in the post anesthesia care unit (PACU) in both groups.
- The intensity of pain at rest and under stress, using a verbal rating scale (VRS), from arrival to discharge from PACU.

- The Silvermann Integrated Approach (SIA) Score (combining pain score and opioid consumption);
- Postoperative outcomes such as postoperative nausea and vomiting (PONV) and amount of antiemetics used in PACU;
- The time spent in PACU (in minutes);

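### The trajectory analysis reads norepinephrine as a response to NOL, although it is titrated to MAP, and its decrease-only classes can never flag a rise in norepinephrine

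*Protocol*

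**What the plan says.** Section E, Drug Perfusion trajectories, standardises each patient's remifentanil and norepinephrine rate using "the mean and standard deviation (SD) of all participants calculated at the same time point". It says the scores grade how important the "intraoperative opioid and norepinephrine administration needed to maintain adequate NOL index" was. Three classes follow, common to both drugs. The first is "None : a decrease in Z score < 1 SD"; Minor is a decrease of at least 1 SD and Major a decrease of at least 1.96 SD. There is no class for an increase, and the reference point for the decrease is not stated.

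Section C, Anesthesia maintenance during surgery, gives the dosing rules. Remifentanil follows the NOL index, with one override: it is also raised "in the event of a TAM > 120% of its basal level, and despite a NOL Index between 10 and 25" (TAM is evidently MAP). For norepinephrine, under the haemodynamic paragraph, the rule is that the "infusion of norepinephrine will be adjusted to maintain +/- 20% of the baseline values of the pre-anesthesia MAP". NOL plays no part in it.

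Three other places bear on the direction of interest. Section A notes that "esmolol can lower BP and HR". Section F lists hypotension among the adverse reactions to esmolol. Section B, Hypotheses, expects opioid sparing "without impacting hemodynamic parameters".

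**The concern.** There are two linked faults. First, a norepinephrine rate reflects what was needed to hold blood pressure. Reading it as what was needed to hold NOL assigns it a meaning that the dosing rule does not give it. For remifentanil the same phrase is only loose, because NOL does drive the dose apart from the MAP override.

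Second, a scale that grades only decreases suits a drug whose use is expected to fall. For norepinephrine the foreseeable esmolol effect is a rise, since esmolol can lower pressure and norepinephrine is what restores it. A rise would count against the hypothesis of no haemodynamic impact, and the planned classes have nowhere to record it. A reader of the trajectory results could see no norepinephrine signal, or one favouring esmolol, while the norepinephrine dose endpoint in Section D shows the opposite.

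**Working it through.** The protocol states no figure for this analysis, so there is none to reproduce. The check applies the written rule and then sizes its effect under stated assumptions.

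**Step 1. Dosing rule against interpretation.**

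| Drug | Titrated to (Section C) | Read as (Section E) | Agreement |
|---|---|---|---|
| Remifentanil | NOL, with a high-MAP override | Needed to keep NOL adequate | Loose but workable |
| Norepinephrine | MAP within 20% of baseline | Needed to keep NOL adequate | Contradiction |

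No readable text doses norepinephrine by NOL. Figure 1 is not shown, but the Section C text is explicit.

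**Step 2. The class rule applied literally.** Put decrease = −(change in Z). Major if the decrease is ≥ 1.96, Minor if ≥ 1, otherwise None.

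| Change in Z | Class |
|---|---|
| −2.5, −1.96 | Major |
| −1.5, −1 | Minor |
| −0.5, 0, +0.5 | None |
| +1, +1.96, +2.5, +3 | None |

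A rise of 3 SD is treated like no change. On the strictest wording a rise is not a decrease at all and belongs to no class. Either way it is not flagged. This holds whether the decrease is a level below the all-participant mean or a fall over time within a patient.

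**Step 3. Size, on one reading only.** Assumptions: a decrease means Z ≤ −1 relative to the all-participant mean; arms are 1:1; rates at a time point are normal with within-arm SD 1; the esmolol mean is higher by d. The protocol gives no norepinephrine rates, so d is shown over a range.

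With the saline mean at 0, the all-participant mean is d/2 and the all-participant SD is √(1 + d²/4). The cut is d/2 − √(1 + d²/4). The share in Minor or Major is Φ(cut) for saline and Φ(cut − d) for esmolol.

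For d = 0.5: SD = √1.0625 = 1.031; cut = 0.25 − 1.031 = −0.781; saline Φ(−0.781) = 21.7%; esmolol Φ(−1.281) = 10.0%.

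| d (within-arm SD) | All-participant SD | Esmolol, Minor or Major | Saline, Minor or Major |
|---|---|---|---|
| 0 | 1.000 | 15.9% | 15.9% |
| 0.2 | 1.005 | 13.5% | 18.3% |
| 0.5 | 1.031 | 10.0% | 21.7% |
| 0.8 | 1.077 | 7.0% | 24.9% |

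By symmetry, at d = 0.5 the shares with Z ≥ +1 are 21.7% for esmolol and 10.0% for saline. The planned classes put none of these patients in Minor or Major; increase classes would show them.

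**Step 4. If rates are not normal.** Infusion rates cannot be negative, so the lowest possible Z is −mean/SD. With a share p of participants on the drug and coefficient of variation c among users, SD/mean = √((1 + c²)/p − 1) ≥ √(1/p − 1), which exceeds 1 when p < 0.5. On the same reading of decrease, nobody could then reach Minor. The percentages in Step 3 would not apply, and the classes would show nothing for norepinephrine at that time point.

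**The case against.** The best defence has four parts.

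- **The scale suits remifentanil.** The hypothesis is a reduction in opioid, and grading reductions as none, minor or major is a coherent scale of sparing. This stands. A reader might infer that the labels run backwards and that Major goes to the lowest rates. That needs the below-the-mean reading. If the decrease is within a patient, a fall from Z = +3 to +1 is a drop of 2, hence Major, while the patient is still above average.
- **The wording is unfinished, not a settled rule.** The section also speaks of nociception Z scores after defining only drug-rate scores, and it does not say what the decrease is measured from. This stands in part. It makes the sign reversal in Step 3 conditional, but it does not rescue the classes, because no reading of a decrease captures a rise.
- **A norepinephrine rise is not established.** The protocol deliberately uses low esmolol doses to limit haemodynamic impact, and at d = 0 nothing is misread between arms. This stands as a limit on size. Since hypotension is a listed reaction, an analysis of norepinephrine should still be able to show a rise if one occurs.
- **Little rests on it.** The classes appear in no objective, hypothesis or endpoint. Norepinephrine dose, mean BP and HR, and time in hypotension are separate secondary endpoints that would show a rise. This stands, and it settles the severity.

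The remaining argument, that class definitions can wait for an SAP, does not hold here: the protocol itself fixes the formula, the cut-offs and the interpretation.

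**Conclusion.** The concern holds as a minor correction. Two elements need no assumption: the NOL interpretation of norepinephrine contradicts its MAP titration, and the decrease-only classes never flag a norepinephrine rise. The analysis therefore cannot speak to the haemodynamic half of the main hypothesis in the direction that matters.

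The apparent reversal between arms (10.0% esmolol against 21.7% saline in Minor or Major) is illustrative. It requires the below-the-mean reading, normal rates and an assumed 0.5 SD rise under esmolol, for which the protocol gives no source.

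A reader might go further and infer that the plan conceals a haemodynamic harm or weakens the trial's main result. The protocol does not support that. The remifentanil comparison and the sample size do not use these classes, and the norepinephrine and hypotension endpoints in Section D are untouched.

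**What to change.** In Section E, Drug Perfusion trajectories:

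1. Describe norepinephrine as given to keep MAP within 20% of baseline, and remifentanil as given under the NOL and MAP algorithm.
2. State that the class is based on Z relative to the all-participant mean at that time point.
3. Label the remifentanil decrease classes as opioid sparing.
4. Add increase classes for norepinephrine (Z ≥ +1 and Z ≥ +1.96) and report them by arm.

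This is a change of wording in one section plus one extra tabulation of rates already planned for collection. Care, blinding, the primary test and the sample size do not change. The cost is a few more sparsely filled classes in about 64 patients (32 per arm).

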## **F. SAFETY AND ADVERSE EVENTS**

### **Safety And Compliance Monitoring**

Ensuring participant safety is a top priority for the research team and hospital staff. In the unlikely chance of an unexpected adverse event, the principal investigator, [name], will be immediately notified. Prompt actions will be taken to provide appropriate care.

The devices used in this study include standard anesthetic monitoring, with the addition of a non-invasive finger probe for NOL analysis. Classical monitoring will always be recorded and serve as the reference for anesthesia guidance.

Patients experiencing adverse reactions will be closely monitored by the appropriate doctor until discharged from the PACU. If necessary, they will be hospitalized for further observation.

### **Medical Monitoring**

The study has a low level of risk. The Principal Investigator (PI) or designated personnel will regularly review all data, such as study completeness, enrollment, protocol deviations, dropouts, and adverse events, on a weekly or bi-weekly basis.

### **Definition Of Adverse Events**

An adverse event is any unfavorable and unintended sign, symptom or disease temporarily associated with the use of a medical treatment or procedure, regardless of whether it is considered related to the medical treatment or procedure. Adverse events will be graded as Mild, Moderate or Severe, and as Related / Possibly Related / Not Related to study procedures.

### **Follow-up of subjects after adverse events**

In the event of beta-blocker overdose or intoxication, the first line of treatment is to administer treatments to accelerate heart rate: atropine, glycopyrrolate or isoprenaline. If these treatments are not effective in treating cardiovascular symptoms, glucagon can be used. Glucagon activates myocardial adenylcyclase, stimulates cyclic AMP synthesis and increases contractility and heart rate, even in the presence of high concentrations of beta-blockers.

Patients included in the research project will be continuously monitored and standardized for general anesthesia. Emergency drugs for rapid treatment of bradycardia or hypotension will be ready and available throughout the patient's stay in the institution. Anesthetists, respiratory therapists and nurses will also be on standby at all times should any of these side effects occur and require urgent treatment. Dealing with these side effects is an integral part of our day-to-day work in the operating theatre and recovery room.

Patients experiencing adverse reactions will be closely monitored by the appropriate doctor. Since esmolol has a 30-minute clearance time, they will benefit from prolonged monitoring for at least 2 hours until discharged from the PACU. Observations during this time will be added to the patient's medical record.

If necessary, they will be hospitalized for further observation. In collaboration with the surgical team, a member of the anesthesia department will visit the patient before he or she is discharged home.

### **Procedures for eliciting reports of and for recording and reporting adverse event and intercurrent illnesses**

In the event of an adverse event, all clinical information and developments concerning the patient will be recorded on the anesthetic and/or postoperative monitoring sheet. These will be integrated into the patient's medical record, along with any subsequent potential clinical assessments.

We'll notify Health Canada within 15 days or 7 days if the reaction is life-threatening or results in death. A detailed report and assessment within the next 8 days, in accordance with Food and Drug Regulations, subsection C.05.014.

An adverse event report will be also be made to CIUSSS EMTL Research Ethics Committee.

### **Administration of the intervention drug : esmolol**

The onset of action of esmolol is short, around 30 seconds, as is its duration of action which revolves between 10 and 30 minutes maximum. Patients will be closely monitored throughout this period, and the risk of adverse effects beyond this point is extremely low.

Standard Canadian Anesthesiologists' Society (CAS) monitoring will be installed before the start of esmolol perfusion and will be maintained until transfer to the recovery room where the patient will also be closely monitored. Emergency medication will be available at the patient's bedside if an adverse reaction occurs.

The use of Esmolol (Brevibloc) has been associated with the following adverse reactions :

- Hypotension : symptomatic hypotension (hyperhidrosis, dizziness) and asymptomatic hypotension
- Bradycardia
- Pulmonary edema
- Bronchospasm
- Administration site reactions some serious in nature. They include signs and symptoms of infusion site irritation and inflammation but also severe reactions ( thrombophlebitis , necrosis and blistering) , in particular when associated with extravasation.

Although esmolol has been used in several studies aiming to reduce intraoperative opioid administration, this indication is not included in the product monograph. Therefore, we sought and received approval (no objection letter) from Health Canada on 2024/02/23.

Subject safety will be guaranteed by research and hospital staff at all times during the completion of the study procedures. All adverse effects will be recorded and patients at risk of serious side effects will be screened and excluded from the present study.

### **G. PROPER HANDLING OF SUBJECTS**

## **Ethical Considerations**

No undiagnosed conditions should be identified in the context of this study. In the inadvertent diagnosis of a new condition, the participant might be excluded, per our exclusion criterias, or remain enrolled based on the manifestation and disease severity. We will file a consultation request to the appropriate physician, for example a vascular surgeon. We will ensure that the required clinical care is appropriately provided to the participant.

## **Subject Withdrawal**

### Early Withdrawal of Patients

We will track the number of withdrawn subjects. Possible reasons a subject may withdraw is a desire to discontinue their participation.

### When and How to Withdraw Patients

A withdrawal occurs when a participant voluntarily chooses to leave or is no longer able to participate in the research study (impossibility to obtain stable NOL Index signal, conversion to laparotomy). We will remove a participant if they mention to the research personnel that they no longer wish to continue with the study. Withdrawal of consent can occur either before the anesthesia, or after once the patient reaches the post-anesthesia care unit (PACU). The research personnel will keep all personal health information secured in the database.

### Data Collection and Follow-up for Withdrawn Patients

We will not store data after participant withdrawal.

## **Breach of protocol**

Three distinct events can lead to a forced breach of protocol during anesthesia : impossibility to obtain stable NOL index signal despite optimization attempts for at least 20 minutes, conversion to laparotomy, or hemodynamic instability. In the improbable event of a major hemodynamic instability potentially attributable to or worsened by the administration of one of the study drugs, the anesthesiologist can decide to stop the protocol.

In all three scenarios, the blinding will be lifted and the perfusion of the research medication will be stopped. These events will be collected and analyzed subsequently.

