### **Randomization and blinding**

Electronic randomization will be performed by a statistician using a computer-generated randomized sequence with a variable block size unknown to the investigators, and then implemented in a RedCAP™ application. It will be sealed in an opaque envelope and handed to the dedicated research staff not involved in patient care and responsible to prepare the blinded syringe. The envelope will be opened at the patient's entry into the operating ward, after confirming that the surgery will be performed. Once the group is assigned to the patient, the research staff will prepare a syringe containing the randomized solution, either esmolol or saline. Each 10ml ampoule contains 100mg of esmolol. Syringe preparation will depend on the patient's adjusted body weight (ABW) and the expected duration of surgery (DOS) in hour as indicated on the surgical booking request. The number of ampoules required (NA) will be calculated according to the following formula (rounded up to nearest whole number):

$$NA = \frac{ABW \times (0.5 + (1.2 \times DOS))}{100}$$

If a syringe recharge is needed during the surgery, a new blinded syringe containing the same substance as the previous one, will be prepared by the dedicated research staff and brought into the operating room.

The patient, the anesthesiologist, the surgeon, the PACU staff and the research team acting as outcome assessors, will all be blinded to the randomization.

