### **Statistical Methods**

Descriptive statistics will be presented by groups using mean and standard deviation, or median and interquartile range if the distribution is skewed or not normal for continuous parameters (according to the skewness of the distribution of each parameter). Frequency (%) will be used for categorical parameters. According to the nature of the analyzed endpoints, confidence intervals (CIs) between proportions or between means/medians differences will be presented. Missing data will be replaced by the maximum value observed (worst-case scenario). Risk differences or mean differences with 95% confidence intervals will be reported for all outcomes. The alpha value will be set at 0.05 to establish statistical significance. All data will be analyzed by the intention to treat principle. All statistical analysis will be performed using SAS, SPSS software or python programming language via VS Code or Jupyter notebook software.

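### Unblinding is mandatory for NOL-signal failure and conversion to laparotomy with no stated need and no limit on who is told, while the protocol conflicts on whether those patients' later data are kept

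*Protocol*

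**What the plan says.** Protocol section G, Breach of protocol, lists three events during anesthesia that force a departure from protocol: "impossibility to obtain stable NOL index signal despite optimization attempts for at least 20 minutes, conversion to laparotomy, or hemodynamic instability". It then orders: "In all three scenarios, the blinding will be lifted and the perfusion of the research medication will be stopped". The section links only the third event to the study medication, speaking of "major hemodynamic instability potentially attributable to or worsened by the administration of one of the study drugs, the anesthesiologist can decide to stop the protocol". It does not say to whom the allocation is disclosed.

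Section C, Randomization and blinding, makes no exception: "The patient, the anesthesiologist, the surgeon, the PACU staff and the research team acting as outcome assessors, will all be blinded to the randomization".

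Several places bear on what happens to these patients' data:

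- When and How to Withdraw Patients counts as withdrawn a participant who "is no longer able to participate in the research study (impossibility to obtain stable NOL Index signal, conversion to laparotomy".
- Data Collection and Follow-up for Withdrawn Patients states: "We will not store data after participant withdrawal".
- Exclusion criteria removes converted patients automatically, after recruitment.
- Statistical Methods states: "All data will be analyzed by the intention to treat principle".
- Breach of protocol ends by saying that the breach events will be collected and analyzed. It does not mention the patients' outcome data.

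**The concern.** A code break is normally reserved for cases where someone needs the allocation to treat the patient. Here it follows automatically from a lost finger-probe signal or a change of surgical approach, and the protocol does not explain why either calls for it.

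The trial is described as double-blinded, and several of its outcomes depend on that. Remifentanil is adjusted by the anesthesiologist, pain is a verbal rating, and hydromorphone is given by the PACU nurse. If these people or the patient know the arm, and the data are analyzed, expectation can enter the comparison. Because the protocol neither limits disclosure nor settles whether the data are kept, a reader cannot tell whether the blind holds for the patients who are analyzed.

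**Working it through.** The plan gives no figure on this point, so the check sets the sections side by side. The only arithmetic concerns the possible number of patients.

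**1. Is a reason for unblinding given?**

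| Event | Tied to the study drug in the text | Reason given for knowing the allocation | Listed as a withdrawal |
|---|---|---|---|
| No stable NOL signal | No | None | Yes |
| Conversion to laparotomy | No | None | Yes (also automatic exclusion) |
| Hemodynamic instability | Yes | Implied by the link | No |

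**2. Does stopping the infusion require unblinding?** The protocol's own text suggests not. The note under Figure 1 allows the blinded syringe to be discontinued in major hemodynamic instability, at the anesthesiologist's discretion, and mentions no code break. Stopping and unblinding can therefore be handled separately.

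**3. Who learns the allocation?** Breach of protocol does not say. The break happens during anesthesia, so the anesthesiologist is the likely recipient, but that is an inference. Nothing says that the patient, the PACU nurses or the assessors are told, and nothing says that they are not.

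**4. Are later data kept?** Three readings are possible for NOL failure and conversion:

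- (a) The exclusion and withdrawal sections prevail. Nothing is stored after the event, so no later outcome can be biased. The code break then has no stated purpose, and removing randomized patients conflicts with intention to treat.
- (b) Intention to treat prevails and the patients are followed. Their later remifentanil and PACU data enter the analysis after the code break.
- (c) Intention to treat prevails but nothing is stored, and the rule in Statistical Methods fills the gap with the maximum observed value. The patients count, but no unblinded observation enters.

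**5. What is exposed under reading (b)?** The primary endpoint is remifentanil from first incision to wound dressing, per kg and hour. With body weight W, duration T, and amounts D1 before and D2 after the code break:

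rate = (D1 + D2) / (W × T)

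D2 is given by an anesthesiologist who may know the arm. After NOL failure, the NOL-guided rule has no input, so D2 rests largely on judgement. In the PACU, the exposed outcomes are the pain rating, time to first analgesic, nurse-given hydromorphone and length of stay.

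**6. How many patients?** The planned total is 2 × 32 = 64. The protocol gives no rate for NOL failure or conversion. As an assumption, take 2% to 15%:

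- 0.02 × 64 = 1.28
- 0.15 × 64 = 9.6

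That is about 1 to 10 patients. It counts code breaks only; the bias per patient cannot be derived from the document.

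**The case against.** The strongest reply is that the specific text answers the worry. NOL failure and conversion are withdrawals, nothing is stored afterwards, and converted patients are excluded. The blinding statement can also be read as the general rule and the breach clause as its exception once the protocol has been abandoned.

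Much of this stands. A reader might infer that PACU outcomes of these patients will be assessed unblinded. The protocol does not support that: it would require both that the data are kept and that the allocation reaches the patient, the PACU staff or the assessors, and neither is stated.

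Two further inferences also fail:

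- *That the 10% dropout allowance gives the number unblinded.* With a difference of 7.98 − 5.59 = 2.39 and SD 3.24, n = 2 × (1.960 + 0.842)² × 3.24² / 2.39² = 28.9, so 29 per group. Then 29 × 1.10 = 31.9, so 32, which reproduces the plan. The allowance is for patients lost to the analysis, so they cannot also be the ones who supply biased data. It is not broken down by cause either.
- *That revealed allocations let staff guess others in the block.* Block size varies and is unknown to the investigators, which leaves little to guess from.

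The objection does not explain why the code must be broken for two events with no stated safety need. It also relies on reading (a), which conflicts with the intention-to-treat statement. If that conflict were resolved in favour of intention to treat with follow-up, and the breach clause were left alone, the exposure would become real.

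**Conclusion.** The point holds in a limited form. The protocol makes unblinding compulsory for two events without a reason and without limiting disclosure, against an unqualified blinding statement. It also contradicts itself on whether the affected patients' later data are used.

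Any bias is conditional. It needs the data to be kept and the allocation to reach someone who treats, rates or reports. For the primary endpoint it is enough that the anesthesiologist is told before remifentanil is stopped. The number affected is unknown; about 1 to 10 of 64 follows only from the assumed 2% to 15%. This should be corrected because the correction is nearly free, but nothing in the document shows that the main comparison is compromised.

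Whether the infusion should stop in these events is a clinical matter and is not judged here.

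**What to change.** Leave the infusion-stopping rules as they are. In Breach of protocol, replace the automatic unblinding with a rule containing three elements:

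- the code is broken only when the treating anesthesiologist needs the allocation to care for the patient;
- PACU staff and outcome assessors stay blinded wherever possible;
- each break is logged with its time, the reason and who was told.

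Add a cross-reference in Randomization and blinding, so that the exception is visible where the blind is promised.

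Then reconcile Exclusion criteria, Statistical Methods, the two withdrawal sections and Breach of protocol, so that one statement settles whether patients with NOL failure or conversion stay in the analysis and whether their later data are collected. If intention to treat stands, the exclusion and non-storage text must be changed for these two events. If the exclusions stand, the intention-to-treat claim must be qualified.

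The cost is one changed sentence, a short log and consistent wording elsewhere. Sample size and study procedures do not change, and emergency unblinding remains available.
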